### Introduction:

Fecal incontinence (FI), defined as the involuntary passage of stool for more than 3 months[1] and is a devastating disease. The negative impact on quality of life has been consistently demonstrated[2-4]. Moreover many patients with FI avoid leaving their homes do to fear of being exposed episodes of FI in public and thus restrict their social life[1]. In the elderly FI may be associated with institutionalization and mortality[5, 6].

The prevalence of FI is probably underestimated in most studies due to unawareness of physicians and patients reluctance to report it to the associated social stigma[7]. Nevertheless the estimated prevalence vary depending on the population studied and the definition of FI [7-11]. In community settings the prevalence of FI increases with age and varies between 2.2 and 25%[12, 13]. In hospitals the prevalence is 18 to 33% and in nursing homes it rises up to 50 to 70%[1]

FI may be secondary to intestinal diseases, pelvic floor disorders, anal weakness, neurological and psychiatric diseases. Often the etiology of FI is multifactorial[1, 13]:

- Anal sphincter weakness
  - Traumatic: obstetric, surgical, others.
    - Obstetric anal sphincter injury can cause immediate FI, but more typically begins 2–3 decades after the injury.
  - Nontraumatic: scleroderma, internal sphincter degeneration of unknown etiology
  - Neuropathy: peripheral (e.g., pudendal) or generalized (e.g., diabetes mellitus)
- Disturbances of pelvic floor: rectal prolapse, descending perineum syndrome
- Disorders affecting rectal capacity or sensation:
  - Inflammatory conditions: IBD, post radiation
  - Rectal surgery: Pouch, low anterior resection
- Central nervous system disorders: dementia, stroke, brain tumors, multiple sclerosis, spinal cord lesions
- Psychiatric diseases, behavioral disorders
- Bowel Disturbances:
  - Diarrhea: irritable bowel syndrome, post-cholecystectomy diarrhea
  - Constipation and fecal retention with overflow.

The management of FI start with reassurance, explaining patients that the disorder is not uncommon. Dietary modifications, skin care, and medications to improve stool consistency and delivery to the rectum may suffice. Anti-diarrheal drugs should provided if diarrhea is present. Pelvic floor training and biofeedback training have been found effective as well[13].

Scheduled defecations (e.g. every morning) with or without water enemas to clean the left colon can benefit some patients.

Minimally invasive procedures such as injection of bulking agents to the anal sphincter and muscle augmentation with radiofrequency ablation (SECCA) as well as surgical interventions and sacral nerve stimulation may be of use to some patients but are complex, expensive and associated with adverse effects.

Consequently local mechanical devices, that can be applied externally are very attractive, some of them are already commercially available.

We developed an "anal tape" using a commercially available elastic band with a special adhesive that is approved for use in the skin. This adhesive band is available worldwide and is used by numerous people, especially athletes. The band can be fashioned in any form and taped to any area of the body with a healthy skin and is for single use. Thus a square of the band with a small opening in the center can be applied to the skin surrounding the anus providing support and additional pressure forces to the anal sphincter.

This study will explore the efficacy and safety of this device in patients with FI, importantly the tape is commercially available; thus we have no commercial interest in the success of the device.

#### **Aims of study:**

To determine the efficacy and safety of the "anal tape" device in patients with fecal insentience that match with the inclusion and exclusion criteria of this study.

#### **Study design:**

This is a 4 week open-label, non-blinded, non randomized study in patients with fecal incontinence.

The study will consist of two periods of two weeks:

- First two weeks - control period: Patients will be asked to continue his / her normal life and to answer to validated questionnaires of fecal incontinence, quality of life and to fill a stool diary.
  - The first week will be considered as the baseline period
  - The second week as the control period.

- Second two weeks - treatment period: Patients will be provided with the device, and ask to answer to the same questionnaires, stool diary and an additional usability questionnaire.

### **Study population**

Male and female patients above the age of 18 suffering from fecal incontinence of any etiology and that match the inclusion and exclusion criteria.

### **Inclusion criteria:**

- $\geq 18$  years old
- Fecal incontinence for more than 6 months
- Willing to participate
- Understand the study procedures
- Is able to apply and remove the "anal tape" without significant assistance of others.
- Have done sigmoidoscopy or colonoscopy and anal manometry within five year of screening visit
  - If there is clinical suspicion of proctitis a new sigmoidoscopy will be required as part of the regular clinical evaluation of patient with suspected proctitis.

### **Exclusion criteria:**

- Advanced full thickness rectal prolapse.
- Injured, inflamed or any significant disease in the peri-anal skin.
- Allergy to any component of the device, either known or developed during testing in the screening visit (see below).
- Moderate to severe proctitis of any etiology.

### **Outcome variables:**

Primary outcomes:

- Any improvement in any of the domain explored by the Fecal Incontinence quality of life questionnaire[14].

Secondary outcomes:

-

- A 50% reduction in the number of episodes of FI or days per week, evaluated with the bowel diary and the weekly Wexner questionnaire.
- Any improvement in Wexner score, both total score and any of its components.
- Any improvement in quality of life score, and in any of its component.
- Usability score
- General satisfaction using a VAS score.
- Willingness of the patient to continue using the anal tape after the study.

Safety outcome:

- Any adverse effect that can be related to the device.

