### **Number of patients:**

In this study each patient will be his own control before and after the intervention. We expected minimal change (if any) during the control period. We calculated that 20 patients in each group are required to have a 80% chance of detecting, (with a significant 5% level), an increase in 5 points in the quality of life questionnaire from 20% in the control period to 60% in the treatment period.

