**Statistical Analysis Plan (SAP):**

Descriptive statistics will be used to define baseline demographic characteristics of patients. Patients' data and clinical parameters will be given as means with standard deviation (SD), for normally distributed variables; and as median with range or interquartile range (IQR) in parenthesis as indicated, for non-normally distributed variables. Differences between the continuous variables during the control and the intervention period will be analyzed by t-test or the Mann-Whitney U test for normally or non-normally distributed variables respectively. Paired, Two-tailed tests with a significance level of 5% will be used in all analyses. All calculations will be performed using IBM statistics SPSS v25.

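### The stated 80% power belongs to a 5-point responder event, not to the written primary outcome, and even for that event the paired power at 20 patients is not fixed

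*Combined protocol and SAP*

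**What the plan says.** Outcome variables gives the primary outcome as "Any improvement in any of the domain explored by the Fecal Incontinence quality of life questionnaire". It sets no minimum change and singles out no domain.

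Number of patients describes a within-patient design, "In this study each patient will be his own control before and after the intervention", and then states the size as for separate groups: "We calculated that 20 patients in each group are required to have a 80% chance of detecting". The effect to be detected is "an increase in 5 points in the quality of life questionnaire from 20% in the control period to 60% in the treatment period". The section does not say whether the 5 points apply to a total or a domain score, and it gives no correlation or discordant proportion between the two periods.

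The SAP section states "Differences between the continuous variables during the control and the intervention period will be analyzed by t-test or the Mann-Whitney U test" and "Paired, Two-tailed tests with a significance level of 5% will be used in all analyses". It names no test for a proportion.

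Study procedures collects the quality-of-life questionnaire on days 0, 7, 14, 21 and 28. Study design calls the first two weeks the control period, then divides them: "The first week will be considered as the baseline period" and "The second week as the control period". No section says which of the five questionnaires enter the control-versus-treatment comparison.

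**The concern.** A power statement is useful only if it refers to the outcome that decides the trial. Here the outcome and the powered event differ in threshold (a change of any size against 5 points) and in scope (any domain against the questionnaire). A reader cannot tell which result would count as success. In an open-label study with several domains and five assessments, that leaves room to settle the claim after the data are seen.

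Pairing is a second problem. The power of a paired comparison of proportions depends on how many patients respond in both periods. Without that figure, the 80% cannot be checked even for the event it was meant for.

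**Working it through.** **1. The two definitions side by side.**

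| | Outcome variables | Number of patients |
|---|---|---|
| Size of change | any | 5 points |
| Scope | any domain | the questionnaire; total or domain not stated |
| Expected rates | none given | 20% control, 60% treatment |

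With no rates for the written outcome, neither a sample size nor a power can be computed for it.

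**2. Reproducing the 20.** Inputs from Number of patients: p1 = 0.20, p2 = 0.60, 5% level, 80% power. The SAP supplies two-sided testing. For two independent proportions with unpooled variance:

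n = (1.960 + 0.8416)² × (0.20×0.80 + 0.60×0.40) / 0.40² = 7.849 × 0.40 / 0.16 = 19.62, so 20 per group.

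Power at 20 per group = Φ(0.40/√(0.40/20) − 1.960) = Φ(0.868) = 80.7%.

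The pooled version gives (1.960√(2×0.40×0.60) + 0.8416√0.40)²/0.16 = 22.33, so 23. The stated 20 therefore matches the unpooled, unpaired formula.

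**3. A paired formula can give the same number.** Let b be the proportion responding in both periods; it can lie anywhere from 0 to 0.20. Then 0.60 − b respond under treatment only, 0.20 − b in the control period only, and the discordant total is d = 0.80 − 2b. The McNemar normal approximation is

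n = (1.960√d + 0.8416√(d − 0.16))² / 0.16.

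- b = 0.20 (d = 0.40): 17.05, so 18
- b = 0.171 (d = 0.458): 19.93, so 20
- b = 0.12, independent periods (d = 0.56): 24.97, so 25
- b = 0 (d = 0.80): 36.79, so 37

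**4. Paired power at 20 patients.** The number of discordant patients is binomial(20, d). Given m of them, those responding under treatment only are binomial(m, (0.60 − b)/d). With k the smaller discordant count and X binomial(m, ½), the two-sided exact p is 2P(X ≤ k), and the mid-p is 2P(X ≤ k) − P(X = k). Summing over all outcomes that favour treatment with p ≤ 0.05:

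| b | Meaning | Exact | Mid-p |
|---|---|---|---|
| 0 | nobody responds in both periods | 45% | 54% |
| 0.12 | periods independent | 62% | 71% |
| 0.16 | 80% of control responders also respond under treatment | 72% | 82% |
| 0.20 | all control responders also respond under treatment | 87% | 95% |

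Both tests pass 80% only towards the top of the range for b, and where they cross depends on the test: about b = 0.18 for the exact test, and already 82% at b = 0.16 for mid-p.

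**The case against.** The strongest defence is that paired intent is explicit. The protocol says each patient is his own control and the SAP requires paired tests throughout, so the wording about groups may be loose drafting. No formula is named, and a paired calculation also gives 20 when about 17% of patients respond in both periods. This stands: the unpaired origin is an inference. What remains is that no dependence is stated.

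The outcome can also be read at group level, as a comparison of mean domain scores between periods, which fits the SAP's tests for continuous variables. That is a fair reading. It turns the loose definition into a multiplicity question across domains, but it still does not match the powered event, which is a proportion.

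Three stronger conclusions might be inferred, and the documents support none of them.

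- **That the trial is underpowered.** The rates for the written outcome are unknown, and for the 5-point event the paired power can lie above or below 80%.
- **That most patients would meet the primary outcome by chance.** Any such rate needs the number of domains, their correlation and the frequency of ties, none of which is given, and it presumes the per-patient reading.
- **That the choice of reference visit changes power by a known amount.** This needs a model of visit-to-visit noise that the documents do not supply.

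It is also fair that this is a small, single-group study and that the remedy is mainly wording.

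**Conclusion.** The concern holds. The mismatch between the primary outcome and the powered event is plain from the text and needs no assumption: the 80% power was not calculated for the primary outcome, and the direction of the error is unknown.

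For the 5-point event at 20% against 60%, two-sided 5% and 20 patients, the 80% is not assured. The ranges above rest on the protocol's own rates, on the full possible range of dependence between periods, and on the choice of McNemar variant, which the documents leave open. The SAP names no test for that event. Pairing does not in itself make 20 too few.

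**What to change.** Use one primary variable in Outcome variables, Number of patients and the SAP. Either of these would serve:

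- **(a)** The proportion of patients with at least a 5-point increase in one named score (the total or a named domain), over equal intervals: day 0 to 14 for control and day 14 to 28 for treatment. Analyse it by a paired McNemar test, with the variant named.
- **(b)** The paired change in one named score, treatment period against control period, by paired t-test or Wilcoxon signed-rank test. The latter replaces the Mann-Whitney U test, which is for independent samples. This option stays closer to the SAP and needs no cut-off.

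State which assessments serve as reference and make the period labels in Study design agree with them. Equal intervals are preferable to a shared day 7 reference, which would set a 7-day change against a 21-day change.

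Restate the power at 20 patients for the chosen paired analysis, with its assumed discordance or SD of differences, even if it falls below 80%. Replace the reference to groups. Make the other domains and visits secondary, either Holm-adjusted or labelled descriptive.

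The cost is wording and a new power statement; no visits, questionnaires or patients are added. The stated power may look less favourable. Open-label bias and regression to the mean remain under either option.

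### Any one quality-of-life domain can meet the primary outcome and each domain is tested at an unadjusted 5%, so on the analysis the SAP specifies the family-wise error exceeds 5%

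*Combined protocol and SAP*

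**What the plan says.** Under Outcome variables, the single primary outcome is "Any improvement in any of the domain explored by the Fecal Incontinence quality of life questionnaire". It names no domain and sets no minimum size of change. The secondary list returns to the same instrument with "Any improvement in quality of life score, and in any of its component", so neither the overall score nor any one domain is ranked above the others.

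The Statistical Analysis Plan states: "Differences between the continuous variables during the control and the intervention period will be analyzed by t-test or the Mann-Whitney U test", according to distribution, and adds: "Paired, Two-tailed tests with a significance level of 5% will be used in all analyses". It contains no multiplicity adjustment, no hierarchy and no test for a binary outcome.

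The Number of patients section describes one comparison. "We calculated that 20 patients in each group are required to have a 80% chance of detecting", at the 5% level, "an increase in 5 points in the quality of life questionnaire from 20% in the control period to 60% in the treatment period". It also says: "In this study each patient will be his own control before and after the intervention".

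**The concern.** A primary outcome that any of several domains can satisfy, analysed by testing each domain score at full 5%, is a set of tests joined by 'or'. Each test has a 5% error rate; the set has a higher one. The sample size is justified as if there were one 5% comparison, so the plan states a level that its success rule does not keep.

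The study is small, open-label and non-randomised, and its primary outcome is self-reported. One domain at p = 0.04 with the others flat could be reported as a positive primary result, and nothing in the plan would require the reader to be told how many domains had the chance to produce it.

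**Working it through.** **1. The plan's own figure.** Inputs from Number of patients: 20% versus 60%, 5% level, 80% power. Two-proportion normal approximation, unpooled variance, two-sided:

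n = (1.960 + 0.842)² × (0.2×0.8 + 0.6×0.4) / (0.6 − 0.2)² = 7.85 × 0.40 / 0.16 = 19.6, rounded up to 20.

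This matches the stated 20. It is not the only formula that could have been used: the pooled version gives 23 two-sided and 18 one-sided. The match is consistent with one two-sided 5% test and no allowance for several domains.

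**2. Inputs for the error rate.** From the documents: 5% per test, two-tailed, paired, 20 patients. Not in the documents, so assumed: number of domains k = 4 (range 2 to 5), and correlation between domain changes 0 to 0.8.

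**3. Independent domains.** The chance of at least one false result is 1 − (1 − 0.05)^k in either direction, and 1 − (1 − 0.025)^k for improvement only.

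| k | Either direction | Improvement only |
|---|---|---|
| 2 | 9.8% | 4.9% |
| 3 | 14.3% | 7.3% |
| 4 | 18.5% | 9.6% |
| 5 | 22.6% | 11.9% |

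**4. Correlated domains.** Simulated normal paired differences with equal correlation and no true change, n = 20, paired t-tests at two-sided 5%, 60,000 trials, k = 4:

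| Correlation | Either direction | Improvement only |
|---|---|---|
| 0 | 18.5% | 9.5% |
| 0.3 | 17.5% | 8.7% |
| 0.5 | 15.9% | 7.9% |
| 0.7 | 13.5% | 6.7% |
| 0.8 | 11.6% | 5.8% |

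For a single test the corresponding figures are 5% and 2.5%. At correlation 0.5, two, three and five domains give about 9%, 13% and 19% in either direction. Over 2 to 5 domains and correlation 0 to 0.8, the two-sided rate runs from about 8% (two domains, 0.8) to about 23% (five domains, 0).

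**5. With Holm adjustment.** Whether at least one domain is significant depends on the smallest p-value, which Holm compares with 0.05/k. For k = 4 that is 0.0125. The simulated family-wise error is about 4.4% at correlation 0.5.

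**6. Power, k = 4, n = 20.** A standardised paired effect of 0.66 gives one 5% test 80% power.
- All four domains carry that effect, correlation 0.5: the chance of at least one significant domain falls from 97% to 87%.
- Only one domain carries it: its power falls from 80% at 0.05 to about 58% at 0.0125.
- On the formula in step 1, 80% power for one domain at 0.0125 needs (2.498 + 0.842)² × 0.40 / 0.16 = 27.9, that is 28 patients rather than 20.

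**The case against.** The strongest objection is that any-domain improvement may define a responder. The Number of patients section is the only place where the quality-of-life effect is quantified, and it compares one percentage with another, 20% against 60%, as a single binary outcome. Several secondary outcomes also read as patient-level results. If each patient is classed as improved or not and the proportions are tested once, there is one primary test and no inflation across domains. This stands as an open reading. It does not remove the point, because the SAP describes tests for continuous variables only, with none for paired proportions. The outcome definition also asks for any improvement while the sample size uses a 5-point increase. The score comparison is therefore the analysis the SAP actually specifies.

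A reader might also infer that the trial's false-positive rate is about three times the stated level. The documents do not support that as a general statement. It needs an assumed number of domains and an assumed correlation, and it counts significant worsening, which could not meet an outcome defined as improvement. For four domains, false improvement alone is 5.8% to 9.6%: under twice a flat 5%, though 2.3 to 3.8 times the 2.5% that one two-sided test allows in that direction. With two domains it does not exceed 5% at all.

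Finally, the study is described as exploring the device, which argues for a measured tone. It still states a 5% level and a primary outcome, and the two should agree.

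**Conclusion.** The point holds in conditional form. On the score comparisons that the SAP specifies, an any-domain primary outcome with unadjusted two-sided 5% tests has a family-wise error above 5%. That direction follows from the documents unless the domains are perfectly correlated. The size does not follow from them. It rests on four assumed domains, 20 patients, normal differences and equal correlation of 0 to 0.8, which give about 12% to 18.5% in either direction, or about 6% to 9.6% for false improvement only. No fixed multiple of 5% can be read from the documents. The finding lapses if the sponsor states that the primary outcome is a per-patient responder rule with one named paired test. Until the text says which reading is meant, the choice could be made after the data are seen, so it should be settled before analysis.

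**What to change.** Add to the Statistical Analysis Plan: *The primary outcome is met if at least one domain of the questionnaire changes in the favourable direction with a Holm-adjusted two-sided p<0.05 across all domains; all domain results and adjusted p-values are reported.*

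This needs wording only, with no new data. Its price is power. With four domains the smallest p-value must fall below 0.0125, which gives the losses in step 6: modest if all domains respond together, substantial if only one does. The sponsor should state that cost and accept it knowingly.

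Naming one domain or the total score as primary would be an alternative that keeps both the 5% level and the 20 patients, at the price of choosing in advance. If a responder rule is intended, the SAP should say so and name one paired test for it.

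Holm adjustment does not settle two neighbouring gaps: any improvement versus a 5-point increase, and which of the questionnaires from days 0, 7, 14, 21 and 28 enter the comparison. Both should be fixed in the same edit.

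### Secondary outcomes: testing the Wexner total and every component at an unadjusted 5%, and repeating the primary quality-of-life domains, leaves the chance of a false improvement uncontrolled at about three to six times the nominal rate

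*Combined protocol and SAP*

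**What the plan says.** Under Outcome variables, the primary outcome is "Any improvement in any of the domain explored by the Fecal Incontinence quality of life questionnaire[14" (reference mark cut off). The secondary list contains three items that compare the control and treatment periods:

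- The item on how often incontinence occurs reads "A 50% reduction in the number of episodes of FI or days per week, evaluated with the bowel diary and the weekly Wexner questionnaire".
- The Wexner item, which has no threshold, reads "Any improvement in Wexner score, both total score and any of its components".
- The item that returns to the questionnaire behind the primary outcome reads "Any improvement in quality of life score, and in any of its component".

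Usability, satisfaction on a VAS and willingness to continue complete the list. Study procedures schedules these three only at day 28. It also schedules a single quality-of-life form at each of days 0, 7, 14, 21 and 28, so the primary and the secondary quality-of-life items draw on the same forms.

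The SAP states: "Differences between the continuous variables during the control and the intervention period will be analyzed by t-test or the Mann-Whitney U test", according to distribution. It adds: "Paired, Two-tailed tests with a significance level of 5% will be used in all analyses". Neither section names a key secondary outcome, a testing order, a multiplicity adjustment or a descriptive status for any outcome.

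**The concern.** The Wexner item has several ways to succeed: the total may improve, or any one component may. Each is tested at the full 5% level. If the tape does nothing, every extra component is another chance of a significant result that can be reported as a secondary outcome met.

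The quality-of-life item adds a different problem. Its component part is the primary outcome over again, from the same answers. One chance result in one domain could be reported once as the primary finding and again as secondary support, although the second report adds no information.

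The study is open-label, non-randomized and sized at about 20 patients, so little else in the design guards against reading too much into one selected component.

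**Working it through.** **The plan's own figures.** The documents state no error rate for the secondary outcomes as a family. The figures available are the 5% two-sided level and the sample size: "We calculated that 20 patients in each group are required to have a 80% chance of detecting, (with a significant 5% level"), for a change in the "quality of life questionnaire from 20% in the control period to 60% in the treatment period". The 20 reproduces from the unpooled formula for two independent proportions:

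(1.960 + 0.842)² × (0.2 × 0.8 + 0.6 × 0.4) / (0.6 − 0.2)² = 7.85 × 0.40 / 0.16 = 19.6, so 20.

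That this formula ignores the pairing is a separate matter. Here 20 serves only as the number of paired patients.

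**Inputs.**

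- Level: two-sided 5%, paired (SAP). A false improvement on one test therefore has probability 2.5%.
- Number of Wexner tests: total plus components. The number of components is not in the documents. Five is assumed, giving six tests.
- Correlation between the six paired changes: not in the documents. The range shown is 0 to 0.8.

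**Independent tests.** P(at least one false significant improvement) = 1 − (1 − 0.025)⁶ = 1 − 0.859 = 14.1%. Counting either direction: 1 − 0.95⁶ = 26.5%.

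**Correlated tests.** Simulated trials of 20 patients with equally correlated normal paired differences, no true effect, and a two-sided paired t-test at 5% on each of six scores gave:

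| Correlation | Any p<0.05, either direction | Any significant improvement | Ratio to 2.5% |
|---|---|---|---|
| 0 | 26.6% | 14.1% | 5.6 |
| 0.5 | 21.4% | 10.8% | 4.3 |
| 0.8 | 14.2% | 7.3% | 2.9 |

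Repeat runs differ by a few tenths of a percentage point. The third column is the relevant one, because the outcome is improvement; the second column also counts significant worsening.

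**A wider family.** If FI episodes and FI days are added as two more paired tests (eight in all), the chance of a false significant improvement is 18.4%, 12.9% and 8.3% at correlations 0, 0.5 and 0.8. These figures are less secure. The FI item is a 50% reduction, which is a responder outcome, and the SAP names tests only for continuous variables.

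**The overlap.** The primary covers any domain of the quality-of-life questionnaire. The secondary item covers the overall score and any component. The components repeat the primary; the overall score does not, because the primary does not mention it.

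**The case against.** The best defence is that these outcomes are labelled secondary and the sample size rests on quality of life alone. The end of the Introduction speaks of exploring efficacy and safety, and unadjusted secondary outcomes are common in a small before-after study. The SAP sentence on the 5% level fixes pairing, sidedness and alpha; it does not rank outcomes. This stands in part. A reader might infer that the secondary outcomes have the same status as the primary, and the separate headings do not support that. But the plan never says what a secondary result may be used for, and Aims of study speaks of determining efficacy. The label alone does not settle the matter.

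A second objection is to size. A reader might infer that a false improvement is likely, or that the excess is about five times the 5% level. The five-times figure comes from counting eight tests in either direction (about 25% at correlation 0.5), so it includes worsening. With improvement only, even independent tests pass one half only at 28 tests (1 − 0.975²⁸ = 50.8%). It is true that the outcome wording sets no threshold. If any mean change above zero counted, six independent measures would show at least one with probability 1 − 0.5⁶ = 98.4%. But the SAP says 5% tests are used in all analyses, so that is not the planned analysis.

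Third, the repetition is only partial, because the overall quality-of-life score is new. That is correct, and the fix allows for it. Fourth, usability, VAS and willingness have no control-period value and so lie outside the family of period comparisons. That is also correct, and none of the figures above includes them.

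**Conclusion.** The point holds as a limited one. As written, the plan lets any one of several Wexner scores count as a secondary improvement at an unadjusted level, and lists the primary domains a second time. For the Wexner item alone, the chance of at least one false significant improvement is about 7% to 14% (10.8% at correlation 0.5) against 2.5% for one test. That is roughly three to six times nominal and uncontrolled, but not likely.

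The figures assume:

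- five components;
- 20 patients;
- equal correlation between scores;
- one control-versus-treatment comparison per score;
- a reading of the Wexner item in which the total and each component are separate outcomes, any of which can be reported as met.

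More components, or several time points per score, would raise the figures; stronger correlation would lower them. The duplication of the quality-of-life domains depends on none of these assumptions.

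**What to change.** In Outcome variables:

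- Replace the Wexner item with the change in Wexner total score, and say that components will be reported descriptively.
- Delete the repeated quality-of-life domains. Keep at most an overall quality-of-life score, provided it is not part of the primary.

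In the SAP, limit the sentence that applies the 5% level to every analysis. For example: *Secondary outcomes will be reported as estimates with 95% confidence intervals and will not on their own support a claim of efficacy.*

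The FI-reduction item can keep its place in the list; the documents give no reason to rank it below the Wexner total. Testing a secondary outcome only if the primary succeeds is optional. It would control error only if the primary's own any-domain rule were corrected as well.

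The cost is wording in two sections, with no extra patients, visits or data. The downside is that a single significant component could no longer be presented as evidence of efficacy.
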